Participants' use of unsecured technologies, such as the closed Facebook page, will be wholly optional. Joining the closed Facebook group will require approval by the study staff, and participant posts to the closed Facebook page will not be visible to Facebook users who are not members of the group. Likewise, the individual's privacy settings will govern how much of their personal information is visible to group members. However, participants will be advised that information shared on Facebook is not secure. Participants will be encouraged to read and understand Facebook's privacy statements and settings before joining the closed group and posting any content to it. They will also be advised that the Garmin vivofit devices and optional app-based trackers have options to share diet and exercise information with others, and that if they choose to use these features, the information shared will be publicly visible. The Garmin vivofit devices do not have a GPS device, so privacy of participant whereabouts will be preserved.

13. Potential Benefits:

The benefits to participants may include losing weight, being regularly physically active and eating healthier (fewer calories and better foods), reduced stress, more energy, improved stamina, better sleep, and generally feeling better. Participating in this program may have other benefits such as lowered chronic disease risk, greater peer support, and the opportunity for participants to learn more about their health, how to count calories, how to select and prepare healthy foods, the health benefits

of physical activity, how to fit physical activity into daily life, accessible activities that can be performed at home or in the community, and stress management, problem solving, and assertiveness skills.

It is hoped that the information gained from this study will contribute to an evidence base for effective weight loss intervention among this underserved population which experiences substantial health disparities. Furthermore, we expect that the study will result in a modified intervention that is widely translatable in the field, given our collaboration with the Diabetes Prevention Support Center and the widespread implementation of the GLB in communities across the nation.

14. Biostatistics: We will use univariate analysis to summarize the measures of program usability and feasibility and examine their distributional properties (Aims 1 & 2). General/generalized mixed modeling analysis(41, 42) will be conducted for the primary and secondary effectiveness outcomes, to assess initial and sustained impacts of the adapted GLB intervention (Aim 3). More specifically, we will evaluate individual growth models for linear/nonlinear change from baseline to 6 months (level-1, time effects), overall group difference (level-2, group effect), and group difference in change (crosslevel, time-by-group interaction effect) (Hypothesis 3.1). Models will be adjusted for demographic variables (e.g. age, gender, ethnicity, disability severity, etc.), particularly if they are imbalanced after randomization, thereby providing more accurate estimates of the intervention impacts. We will also fit separate individual growth models for change from baseline to 12 months within both groups combined (time effects only) (Hypothesis 3.2). Our data will include missing observations due to either attrition or nonresponse. Intent-to-treat analysis will use restricted maximum likelihood estimation, which can produce unbiased estimates under the conditions of incomplete data. Subsequent intent-totreat analysis will utilize iterative Monte Carlo Markov Chain multiple imputation. (43) This approach includes all selected variables into the imputation process, which allows for greater recovery of the missing data.(44) All analyses will be performed using R(45) and SAS 9.3.(46) Secondary analyses will examine intervention effects for study completers who meet defined program adherence criteria.

Sample size and power. Sample size was determined to provide sufficient power for our analyses on the primary outcomes. Previous studies showed that in general DPP translation efforts including the GLB yield large impacts on weight (median d = 0.99 at 3 months, 0.91 at 6 months, 0.74 at 12 months(16, 17, 19-21, 27, 47-49)) and relatively large impacts on PA (d = 0.69 at 3 months(20)). Results also indicated, at most, 16%, 23%, and 33% attrition at 3, 6, and 12 months, respectively. A sample size of 64 will allow greater than 90% power to detect a conservatively assumed group difference of 4% in weight change (95% power) and 80 min./week in PA (92% power). In the event of 33% attrition (the maximum observed in previous GLB studies), we will achieve 83-87% power to detect these differences. Thus, 64 participants (32 per group) will be enrolled.

References

- 8. Centers for Disease Control and Prevention. Physical activity among adults with a disability-United States, 2005. Morbidity and Mortality Weekly Report 2007;56(39):1021-1024.

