The study will take place over 3 years and consists of two phases. Phase 1 will involve using community-based participatory research (CBPR) to adapt the evidence-based GLB program to assure the needs of people with mobility impairment are appropriately addressed. Phase 2 will consist of a RCT to assess feasibility and effectiveness of the adapted GLB program on primary (i.e., weight and PA) and secondary health outcomes (i.e., waist circumference, upper arm circumference, BP, A1c, serum lipids, self-efficacy, function, and QOL). In Phase 2, 64 individuals (32 per group) with physical disabilities will be recruited via organizations that provide services to those with disabilities and randomized to an intervention group or a 6-month wait-list control group. To ensure the participation of 64 individuals, up to 75 eligible individuals will be consented. We expect to obtain sufficient participants to enroll everyone with the same start date, but if necessary, the study may be conducted among 3 cohorts with staggered start dates.

Phase 1. Adapting the GLB and assessing usability. We will use CBPR to adapt the GLB in iterative fashion guided by input from a 12-member **Advisory Board** comprised of community stakeholders. Members represent people with mobility impairment from the independent living community and scientists, plus health professionals. Board members will receive a small honorarium for their time.

The board will guide the team's efforts in adapting the GLB materials and content in year 1 and provide ongoing input and direction over years 2 and 3 as the team delivers the intervention and assesses its effects.

Phase 2. Assess feasibility and effectiveness of the adapted GLB for people with mobility impairment. A two-group (experimental and wait-list control), RCT will assess feasibility of delivering the intervention and its effectiveness on primary and secondary outcomes. Those assigned to the **control group** will wait 6 months before receiving the intervention. During the 6 month waiting period, the control group will be mailed monthly newsletters that address topics of making healthy lifestyle choices (achieve good sleep; reduce stress; spend time with friends; follow recommended schedule of vaccines & cancer screening; reduce risk of common conditions such as pain, depression; know your rights).

GLB intervention.

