Origin and format. The GLB program selected for this proposed study was translated directly from the successful multi-center DPP. Study co-investigator, Dr. [name] directs the Diabetes Prevention Support Center (DPSC) at the University of Pittsburgh, where the DPP lifestyle intervention was initially developed. [name] and colleagues adapted and updated the original 16 session one-on-one DPP to a group-based format consisting of 12-weekly core sessions followed by 4 biweekly core and 6 monthly support sessions, for a total of 22 sessions delivered over one year. Other modifications included emphasizing self-monitoring of calories and fat intake from the beginning of the intervention and an enhanced focus on pedometer use. The GLB program has been successfully delivered in numerous settings (e.g., health care, (16, 17, 27-29) YMCA,(30) churches,(31) community centers(32, 33)), with various populations at risk for diabetes, and has been offered in person and via DVD.(27, 28)

Components. The intervention encourages participants to adopt a moderate calorie, moderate fat diet (1200-2000 calories, depending on start weight, with \leq 25% of calories from fat) and to increase exercise progressively to meet ACSM/AHA recommendations of 150 minutes per week. The program facilitates the accomplishment of these goals by teaching skills including self-monitoring, problem solving, assertiveness, cues, and stress management. Participants are encouraged to set a weight loss goal of 7%. Coaches facilitate skillbuilding and provide positive reinforcement, while group members offer peer support.

Modifications. The proposed study will follow the 12-month GLB schedule for delivering the adapted GLB. The anticipated plan for implementation is to initiate the program with an in-person instructional kickoff meeting and the deliver the content primarily through telephone conference calls, with once a month in-person meetings offered. The content includes **6 primary components**. Participants will be:

- 1) Given the modified GLB curriculum materials, adapted in response to Advisory Board input to make them appropriate for the mobility impaired audience;

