 - 2) Invited to participate in teleconference-based group meetings, delivered in accordance with the GLB schedule and led by a trained lifestyle coach; meetings will be offered via a videoconferencing technology, such as Adobe Connect, which allows people to connect by landline, cell phone, tablet, or computer and connect either via audio alone or audio and video.
 - **3)** Invited to an optional in person meeting each month, during which participants can be weighed;
 - 4) Offered monthly individualized phone support from a lifestyle coach;
 - 5) Invited to include caretakers or key family support in meetings, if desired
 - **6)** Offered exercise aids that are appropriate for individuals with impaired mobility, including disability appropriate exercise DVDs, Garmin vivofit arm-based exercise trackers with heart rate monitors, pedal exercisers, and therabands (versus the GLB's offering of nonmodified exercise DVDs, pedometers, and other incentives). Participants will also be given Calorie

King™ calorie counting books, measuring cups, and a scale, in accordance with the mainstream GLB.

Conditions that may result in the subject exiting the study before the expected completion date include subject withdrawal of consent or decision not to continue their participation. Because of the remote nature of the intervention, participants may choose to continue the study despite adverse health events including hospitalization. However, participants will be explicitly advised to follow their doctors orders in all matters, including those most relevant to the study—physical activity and diet.

Outcome measures.

Feasibility measures will assess participants' adherence with key intervention components: **1)** group meeting attendance, **2)** individualized phone call attendance, and **3)** for the first 12 weeks only, self-monitoring of food intake and PA.

Effectiveness measures. **Primary outcomes** to assess the GLB effects will be collected at baseline and again at 3, 6, and 12 months. These will include participant's weight, PA, self-efficacy, function, and QOL. **Secondary outcomes** will be measured at baseline, 6, and 12 months and will include waist circumference, BP, A1c, serum lipids.

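### If outcomes are correlated within the intervention arm's meeting groups, the planned 0–6 month comparison understates its standard error, and neither the model nor the power statement allows for it

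*Combined protocol and SAP*

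**What the plan says.** Section 3 (Modifications) has intervention participants invited to teleconference-based "group meetings, delivered in accordance with the GLB schedule and led by a trained lifestyle coach". Under Components, coaches build skills "while group members offer peer support". Section 4 (Venue, Communication) adds in-person sessions and an optional closed Facebook page, both meant to foster cohesion among participants. For the first six months the control arm receives monthly newsletters by mail and no group contact (section 3, Phase 2).

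On timing, section 3 expects everyone to begin on one date; only if recruitment requires it, "the study may be conducted among 3 cohorts with staggered start dates". No section gives the number or size of meeting groups.

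Section 14 (Biostatistics) specifies a growth model with time at level 1 and treatment arm at level 2, plus their interaction. What it calls the group effect is the arm. No term for meeting group, coach or start cohort is named.

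The sample-size paragraph says "A sample size of 64 will allow greater than 90% power": 95% for a 4% difference in weight change and 92% for 80 min/week of physical activity (PA), and "64 participants (32 per group) will be enrolled". It gives no alpha, standard deviation, power method, ICC or design effect.

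**The concern.** For Hypothesis 3.1 this is a partially nested design: intervention participants share a coach, sessions and peers, while wait-list participants do not. The protocol presents interaction among members as part of how the programme works, so some similarity of outcome within a meeting group is plausible. A two-level model sets that correlation to exactly zero. If it is positive, the interval for the treatment effect is too narrow and the test rejects too often when the average effect is nil. This touches the central effectiveness claim, which section 1 says is to support a large-scale trial. The stated power would also hold only at zero correlation.

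**Working it through.** **Inputs.** From the documents: 32 per arm; power 95% (weight) and 92% (PA); for weight, "median d = 0.99 at 3 months, 0.91 at 6 months, 0.74 at 12 months"; for PA, d = 0.69 at 3 months. Assumed: two-sided alpha 0.05; ICC 0.01–0.05; one, two or three equal meeting groups; no attrition. The growth-model contrast is approximated by a two-sample comparison of change.

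**Step 1: the plan's own figure.** With 32 per arm the noncentrality is d × √(32/2) = 4d. At d = 0.91 it is 3.64, and a two-sided t test on 62 df has 94.8% power. This matches the stated 95% under independence. At d = 0.69 power is 78%, so the 92% for PA is not reproduced. Solving backwards from the stated power gives d = 0.916 (implied SD 4/0.916 ≈ 4.4 percentage points) and d = 0.855 (80/0.855 ≈ 94 min/week). These two effect sizes are back-solved and do not appear in the plan.

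**Step 2: standard error and type I error.** With m members per group, the intervention-arm variance is multiplied by DE = 1 + (m − 1) × ICC; the control arm is unchanged. The variance of the difference is multiplied by A = (DE + 1)/2, and the true SE is √A times the SE of the planned model. Type I error = 2 × P(Z > 1.96/√A).

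| Groups (m) | ICC | DE | A | √A | Type I error |
|---|---|---|---|---|---|
| 3 (10.7) | 0.01 | 1.097 | 1.048 | 1.02 | 5.6% |
| 3 (10.7) | 0.05 | 1.483 | 1.242 | 1.11 | 7.9% |
| 2 (16) | 0.01 | 1.150 | 1.075 | 1.04 | 5.9% |
| 2 (16) | 0.05 | 1.750 | 1.375 | 1.17 | 9.5% |
| 1 (32) | 0.01 | 1.310 | 1.155 | 1.07 | 6.8% |
| 1 (32) | 0.05 | 2.550 | 1.775 | 1.33 | 14% |

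**Step 3: power, by analysis.** With three groups and ICC from 0.01 to 0.05, power depends on which analysis is meant:

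| Analysis | Weight | PA |
|---|---|---|
| Planned model, uncorrected SE | 95–93% | 92–90% |
| Design-effect approximation: d/√A, t on 62 df | 94–90% | 91–86% |
| Partially nested, Satterthwaite df | 86–76% | 82–71% |

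The first row stays high because the test uses too small an SE, which is the source of the excess type I error. For the third row, df = (DE + 1)² / [DE²/(g − 1) + 1/31] with g groups. At g = 3 and ICC 0.05 this is 2.483²/(1.483²/2 + 1/31) ≈ 5.4. Part of the loss there is the price of few groups: for PA the same model gives 84% at ICC 0. With one group the between-group variance cannot be estimated, so the third analysis does not exist.

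**The case against.** The strongest reply is that everything quantitative is conditional. No ICC is documented, and at 0.01 with three groups the design-effect approximation costs about one percentage point of power. Mainly remote delivery, optional in-person meetings, individual phone support and recordings of missed sessions may all weaken within-group correlation. This stands, and it is why the size is given as a range.

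Second, type I inflation is not automatic. If the programme changes nobody's outcome, individual randomisation leaves no correlation created by delivery. Excess false positives need a zero average effect together with real differences between groups. This also stands. When the programme does have effects that vary by group, however, the interval is too narrow by the same factor √A.

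Third, a reader might infer from the cohort sentence that the trial will run in three one-arm clusters. The documents do not support that: cohorts are a fallback, and nothing says a cohort would hold only one arm. Start cohorts are calendar blocks, and adjusting for them does not address clustering within the intervention arm.

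Fourth, section 7 calls this a pilot study, and a group variance from two or three groups is very imprecise. That argues for a sensitivity analysis rather than a new primary model. It does not justify leaving the zero-correlation assumption unstated.

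**Conclusion.** The omission is real: delivery in the 0–6 month comparison is partially nested, and neither the model nor the power paragraph allows for it. For any positive within-group correlation the planned standard error is too small. At an assumed ICC of 0.01–0.05 the type I error is about 5.6–7.9% with three groups, 5.9–9.5% with two, and 6.8–14% with one.

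A reader might go further and conclude that the standard errors are too small and the power overstated as a matter of fact. The documents do not support that, because they give neither the ICC nor the number of groups. That the power calculation assumed independence is also an inference: the weight figure fits it, while for PA it rests on the plan's silence. The results depend on the assumed two-sided alpha, and the power figures also on the back-solved effect sizes.

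The one-arm description applies to Hypothesis 3.1. For Hypothesis 3.2 both arms will have received group delivery, so any clustering then affects the whole sample.

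**What to change.** 1. State the planned number and size of meeting groups and record each participant's membership. With two or more groups, add a sensitivity analysis for Hypothesis 3.1 with a random meeting-group effect in the intervention arm only and small-sample degrees of freedom; report the estimated correlation and call it imprecise. With a single group, show the treatment-effect interval widened by √A over an assumed ICC range, and state that the group variance cannot be estimated.
2. If the three-cohort fallback is used, randomise within cohort and include start cohort as a fixed effect in the Hypothesis 3.1 models. This handles calendar differences only.
3. State that the 95% and 92% power assume zero within-group correlation. Any range offered must name its analysis: with three groups, 94–90% (weight) and 91–86% (PA) by the design-effect approximation, but about 76% and 71% at ICC 0.05 with small-sample degrees of freedom. Disclose that 0.916 and 0.855 are back-solved from the stated power at an assumed two-sided alpha of 0.05.

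The cost is some added wording, one extra model, an imprecise group variance and a less favourable power statement. The primary model and the sample size do not change.

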Baylor Institute for Rehabilitation Institutional Review Board

Protocol Template (for Investigator Initiated Studies)

Title: Group Lifestyle Balance Adapted for Impaired Mobility (GLB-AIM): Translating the GLB to Promote Healthy Weight in People with Mobility Disability (Impairment)

1. Introduction and Purpose:

This study will test **the effectiveness of the Group Lifestyle Balance**™ (GLB) program **adapted specifically for people with impaired mobility** using standard behavioral approaches for weight loss. The overarching aim of this study is to promote health and reduce chronic disease risk among people with mobility impairment by building an evidence base for weight loss. Our central hypothesis is that participants randomized to the intervention arm of the adapted GLB will show significant improvements on primary outcomes of weight and PA compared to a 6-month wait-list control group at 3 and 6 months, and will show improvements on several secondary health outcomes.

We propose the following specific aims and hypotheses:

Aim 1: To create an appropriate and usable adaptation of the GLB program for people with mobility impairment.

Hypothesis 1.1: Advisory board participants will identify key adaptations to make the GLB materials appropriate and usable for individuals with impaired mobility.

Aim 2: To establish whether the adapted GLB program for people with mobility impairment is a feasible intervention.

Hypothesis 2.1: Intervention participants will rate the program satisfactorily and attend at least 2/3rd of the weekly group-based meetings and monthly individualized phone calls. Lifestyle coaches will also rate the adapted program satisfactorily.

Aim 3: To determine if the GLB intervention adapted for those with mobility impairment is effective as determined by significant improvement in the primary and secondary outcomes in the intervention group compared to the wait-list control group at 3 and 6 months from baseline.

Hypothesis 3.1: The intervention group will demonstrate significantly greater improvements in our primary outcomes (weight and PA) than the wait list control group at 3 and at 6 months and will show significant improvements in secondary outcomes at 6 months.

Hypothesis 3.2: Both groups combined will demonstrate significantly greater improvements in the primary outcomes (weight and PA) after 3, 6 and 12 months of intervention and secondary outcomes after 6 and 12 months of intervention.

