Visits. Participants in the experimental group will be tested at baseline, 3 months, 6 months, and 12 months. Participants in the 6 month wait-list control group will be tested at baseline, 3 months, and 6 months, (for comparison to control group) and again at 9 months, 12 months, and 18 months (to assess intervention). Testing will be conducted in a private room at [name] research office at Baylor Institute for Rehabilitation Labwork will be processed at a UTSouthwestern lab, with

costs paid for by the study. All other testing will be performed by the PI, the trained program coordinator, or the trained research assistant. We estimate that the first visit will last approximately 1,5 hours, and each subsequent visit will last approximately 1 hour.

All visits (Baseline, 3 months, 6 months, 12 months):

- 1) Study staff will measure participants' weight using an accessible Seca scale (#676).(34) Weight for wheelchair users will be conducted first by measuring the total weight of the person in their wheelchair, the person will then transfer out of the chair to a mat table and those unable to transfer will be raised from their chair using a Hoyer lift, then the wheelchair will be weighed separately without the person in the chair. Patients who do not require a Hoyer lift but who do require assistance in transferring from their chair will to a mat table be assisted by study staff, who have been trained by physical therapists in performing transfer assists. The weight of the wheelchair will be subtracted from the total weight. Finally, staff will ask participants to report the use of any medications to control blood pressure or cholesterol, or any medications that may influence weight (such as certain medications to treat depression/anxiety, diabetes, or pain).
- 2) Participants will be asked to complete a pencil/paper questionnaire to measure self-reported physical activity (using the IPAQ short form), self-rated health abilities (SRAHP), quality of life (SF36E(35)), and to report on any change in medications that may influence weight, cholesterol, or blood pressure.

Baseline only:

- 1) Height will be measured with participants in a supine position when possible. Participants who have higher level injuries and/or difficulties in lying down will be asked to self-report their height.
- 2) Participants will be asked to complete a pencil/paper survey to gather demographic information; weight loss history; and history of common health complications.

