Baseline, 6 months, and 12 months:

- 1) Study staff will measure participants' blood pressure using an automatic cuff (Omron 7 Series wrist blood pressure monitor); upper arm circumference, and waist circumference measured at the umbilicus, with participants in a supine position when possible. Participants who have higher level injuries and/or difficulties in lying down will be measured in a seated position, or if they choose, transferred to the mat using a Hoyer lift.(34) Patients who do not require a Hoyer lift but who do require assistance in transferring from their chair will to a mat table can choose to be assisted by study staff, who have been trained by physical therapists in performing transfer assists.
- 2) A phlebotomist will draw participants' blood via venipuncture, and a UTSW lab will measure serum lipids to assess cardiovascular disease risk, A1c to assess participants' average blood sugar level over the past 2-3 months, and albumin to assess blood protein levels and nutritional status. The total volume of blood drawn will be 10mL, collected in 2 vials of 4-5 mL each.

Baseline and final visit (12 months for experimental group, 18 months for control):

 In addition to the above, participants will be asked to answer paper/pencil survey questions to assess the following: functional abilities in activities of daily living and instrumental activities of daily living (using the LIFE-H short form questionnaire);

- functional abilities around diet, eating, and fitness (using portions of the LIFE-H long form); and types of physical activities (using the 1-year MAQ).
- 2) Structured interviews with participants, conducted either in person or by phone, will gather qualitative information on topics such as motivation for joining the program; past weight loss experiences; who selects, purchases, and prepares food in the home; changes in these roles over time; the process of lifestyle change and its effects on sense of self and relationships; and barriers and facilitators to change. Similar questions may be asked and responses gathered during one or more of the monthly individualized phone support calls throughout the course of the program. Interviews may be recorded to ensure participant responses are accurately captured.

Final visit only:

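### The Outcome measures text makes self-efficacy, function and QOL primary, against the rest of the plan, and the visit schedule leaves function without a 6-month value for the wait-list comparison

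*Combined protocol and SAP*

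**What the plan says.** **Labels.** The opening of section 3 divides the outcomes into "primary (i.e., weight and PA) and secondary health outcomes (i.e., waist circumference, upper arm circumference, BP, A1c, serum lipids, self-efficacy, function, and QOL". Later in section 3, under Outcome measures, the Effectiveness measures paragraph opens with the primary outcomes, to be collected at baseline, 3, 6 and 12 months, and continues: "These will include participant's weight, PA, self-efficacy, function, and QOL". Its secondary list (waist circumference, blood pressure, A1c, lipids) is scheduled at baseline, 6 and 12 months.

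**Claims.** In section 1, Aim 3 looks for "significant improvement in the primary and secondary outcomes in the intervention group compared to the wait-list control group at 3 and 6 months". Hypothesis 3.1 expects "significantly greater improvements in our primary outcomes (weight and PA) than the wait list control group at 3 and at 6 months" and that the intervention group "will show significant improvements in secondary outcomes at 6 months". Hypothesis 3.2, for both groups combined, covers "secondary outcomes after 6 and 12 months of intervention".

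**Schedule.** In section 4, the questionnaire given at all visits contains the IPAQ short form, "self-rated health abilities (SRAHP), quality of life (SF36E(35"). LIFE-H appears under a different line: "Baseline and final visit (12 months for experimental group, 18 months for control"). Controls start the intervention after a 6-month wait.

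**Analysis.** Section 14 fits growth models from baseline to 6 months with a time-by-group term for Hypothesis 3.1. It states power for weight (95%) and PA (92%) only.

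**The concern.** There are two separate problems.

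The first is the label. With two definitions of primary in one section, a significant QOL result alongside null results for weight and PA could be reported as a primary success under one paragraph and as a secondary finding under the other. The sample size was not justified for QOL.

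The second is function. The paragraph that makes it primary also says it is measured at 3, 6 and 12 months, and the detailed schedule does not provide for that. If staff follow the detailed schedule, any statement that the programme improved function relative to the wait-list group would have no untreated follow-up behind it. This cannot be repaired afterwards: once controls begin the intervention, their untreated 6-month value is lost. No mixed model or imputation can recover a visit at which nobody in either group was measured.

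**Working it through.** **1. Which label is the outlier?**

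| Place | Primary outcomes |
|---|---|
| Section 1, central hypothesis, Hypotheses 3.1 and 3.2 | weight, PA |
| Section 3, opening | weight, PA |
| Section 3, Effectiveness measures | weight, PA, self-efficacy, function, QOL |
| Section 14, sample size | power given for weight and PA only |

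The Effectiveness measures paragraph stands alone.

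**2. When is each disputed outcome measured, according to section 4?**

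| Outcome | Instrument | Experimental (months) | Control (months) |
|---|---|---|---|
| QOL | SF36E | 0, 3, 6, 12 | 0, 3, 6, 9, 12, 18 |
| Self-efficacy (assumed) | SRAHP | 0, 3, 6, 12 | 0, 3, 6, 9, 12, 18 |
| Function | LIFE-H | 0, 12 | 0, 18 |

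The all-visits heading lists baseline, 3, 6 and 12 months. The control times come from the Visits paragraph. The plan does not name SRAHP as the self-efficacy measure, so that row is an assumption.

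**3. Which claims can function support on that schedule?** Controls are untreated from month 0 to month 6.

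- Aim 3, against wait-list at 3 and 6 months: no LIFE-H value at either time in either group. Not testable.
- Hypothesis 3.1, secondary outcomes at 6 months: the time-by-group effect over months 0 to 6 cannot be estimated from baseline values alone. Not testable.
- Hypothesis 3.2, after 6 months of intervention: this is month 6 (experimental) and month 6 + 6 = 12 (control). No LIFE-H at either. Not testable.
- Hypothesis 3.2, after 12 months of intervention: month 12 (experimental) and month 6 + 12 = 18 (control). LIFE-H is given at both, so a before/after estimate is available. In controls the earlier value is from month 0.

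**4. The plan's own figures.** The only figures tied to the primary outcomes are the 95% and 92% power. No SD, alpha or sidedness is stated, so they cannot be reproduced from the plan's inputs. With 32 per group and two-sided 0.05 assumed, power = Φ(d√(32/2) − 1.96). The cited 6-month weight effect, d = 0.91, gives Φ(3.64 − 1.96) = 95.4%. The cited PA effect, d = 0.69, gives Φ(2.76 − 1.96) = 78.8%. A power of 92% needs d = 0.84, an SD of about 80/0.84 = 95 min/week. Nothing below depends on this.

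**5. What could the mislabel do to the false-positive rate?** Assumptions, none stated in the plan: two-sided alpha 0.05, one time-by-group test per outcome, success if any one primary outcome is positive, and equal correlation ρ between test statistics.

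For ρ = 0 the rate with k outcomes is 1 − 0.95^k. For ρ > 0 it is 1 − P(all |Z| < 1.96), by numerical integration over the shared normal factor. The mislabel's own share is P(weight and PA both negative) − P(all outcomes negative).

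| ρ | Weight, PA | + QOL | + QOL, SRAHP | Share, QOL | Share, QOL or SRAHP |
|---|---|---|---|---|---|
| 0 | 9.75% | 14.26% | 18.55% | 4.51% | 8.80% |
| 0.2 | 9.65% | 13.97% | 18.02% | 4.33% | 8.37% |
| 0.5 | 9.08% | 12.54% | 15.58% | 3.47% | 6.51% |

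Check at ρ = 0: 14.26 − 9.75 = 4.51 and 18.55 − 9.75 = 8.80. Function is left out because it has no test to run on the section 4 schedule. If every primary outcome must be positive, the rate is at most 5%.

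**The case against.** The label conflict largely resolves itself. Sections 1 and 14 and the opening of section 3 all point to weight and PA. Section 14 uses the same modelling approach for primary and secondary outcomes, so the label changes how results are described and no calculation. The stray paragraph may simply have sorted outcomes by visit schedule. This stands as a reason to grade the label as a drafting error. It does not remove the error: the paragraph says primary, and sorting by schedule does not explain function, which section 4 does not place at those visits.

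One could also say that SF36E might supply function. Section 4 assigns it to quality of life, and the plan nowhere designates it, or part of it, as the function outcome.

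Several stronger readings are tempting and are not supported:

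- *Function is simply not measured at 3 or 6 months.* Section 3 says it is. The documents contradict each other, and the conclusion is conditional on section 4 being followed.
- *Function cannot be analysed at all.* The 12-month part of Hypothesis 3.2 can be.
- *Self-efficacy and QOL share the gap.* SRAHP and SF36E are given at 3 and 6 months in both groups, so only their label is in conflict.
- *The trial carries a 9-18% false-positive rate because of the mislabel.* That range needs an any-one-positive rule the plan does not state, and the 9.1-9.8% for weight and PA exists without any mislabel. Hypothesis 3.1 joins weight and PA with "and", which fits an all-required rule equally well.
- *The unstated alpha and success rule make this graver.* They are missing detail and partly a matter of choice, in a study that section 7 calls a pilot.

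**Conclusion.** The point holds and should be fixed. It is not a fatal flaw.

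The label contradiction and the schedule contradiction follow from the text and need no statistical assumption. If section 4 is followed, function has no untreated post-baseline value in controls and no 6-month value in either group. The between-group claims of Aim 3 and Hypothesis 3.1, and the 6-month claim of Hypothesis 3.2, then cannot be tested for function. This rests on LIFE-H being the function measure, as its description in section 4 indicates.

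The size of the label problem depends on the success rule. Under an any-one-positive rule at two-sided 0.05 with correlations of 0 to 0.5, the mislabel alone adds 3.5-4.5% through QOL, or 6.5-8.8% if SRAHP is also counted. Under an all-required rule the total rate is at most 5%. The power statements for weight and PA are untouched.

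**What to change.** 1. In the Effectiveness measures paragraph, make weight and PA the only primary effectiveness outcomes and list self-efficacy, function and QOL as secondary. Add a separate schedule line keeping SRAHP and SF36E at all visits, including 3 months. Without it, moving them into a list scheduled at baseline, 6 and 12 months would create a new conflict with section 4. Name the self-efficacy instrument. Cost: text only.

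2. Reconcile sections 3 and 4 on function, in one of two ways:
   - Give LIFE-H at 6 months in both groups: up to 2 × 32 = 64 extra questionnaires, plus up to 32 at month 12 in controls if the 6-month claim of Hypothesis 3.2 is to cover function. This lengthens visits estimated at about one hour, and is useful only if decided before participants pass the 6-month visit.
   - Or state that no between-group claim and no 6-month claim will be made for function. Cost: text only, and a narrower Aim 3.

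3. Secondary, and not part of the grading: state alpha and a success rule for Hypothesis 3.1 in section 14 before outcome data are examined. An all-required rule needs no alpha adjustment but lowers power. From the plan's figures, and taking the two tests as independent, joint power is 0.95 × 0.92 = 87% with full data and 0.87 × 0.83 = 72% at 33% attrition.

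None of these changes needs more participants.
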